2.5.1. Primary Endpoint

The primary endpoint will be assessed 48 hours after randomization.

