### 7.3. Interventions

#### 7.3.1. Methylnaltrexone dosage and treatment duration

To ensure standardization of the protocol, patients with AP will be treated with methylnaltrexone or placebo intravenously for the first 5 days of admission and assessments of endpoints will be done at fixed time points during this period. The dosage will be weight adjusted. Thus, 0.15 mg/kg methylnaltrexone or a corresponding volume of matching placebo (Ringer's lactate) will be dissolved in 1000 mL Ringer's lactate solution and given as a continues infusion over 24 hours using an infusion pump. In accordance with the summary of product characteristics for methylnaltrexone, a 50 % dose reduction will be made for patients with an eGFR below 30 ml/min/1,73m^2. the continuous infusion of study medication will be started no later than 24 hours after preparation. This will be ensured by keeping detailed record on the time of preparation

as well as time of infusion start. As methylnaltrexone is sensitive to light, the solution will be kept protected from light from the time of preparation until the time of infusion start. Two persons trained in the protocol and delegated to do so, will prepare the solution of study medication together. This will be done with one person assisting virtually in exceptional cases.

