## 7.4. Outcomes

### 7.4.1. Primary endpoint

Difference in Pancreatitis activity scoring system (PASS) score between the methylnaltrexone group and the placebo group 48 hours after randomization

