## 7.5. Participant timeline

### 7.5.1. Study days

A detailed description of the study procedures is illustrated in Table 1. Patients will be evaluated daily during admission by medical personnel and treated in agreement with the IAP/APA evidence-based guidelines for the management of AP (2). As part of the study, they will receive daily infusions with methylnaltrexone or matching placebo, and have the following examinations performed: i) clinical outcome and patient symptoms will be evaluated by means of both well-validated questionnaires and information from the patient's medical records (see section 9.1.2.), ii) the PASS score will be obtained daily and used to document the primary endpoint 48 hours after randomization, iii) blood samples (including C-Reactive Protein (CRP), interleukin (IL)-6, IL-8, IL-18, tumor necrosis factor alpha (TNF- $\alpha$ ) and cluster of differentiation 163 (CD163)) will be drawn

daily with the purpose of evaluating the systemic inflammatory response, and iv) an abdominal contrast-enhanced CT study will be performed at inclusion and after conclusion of treatment at day 5 (+/- 1 day) to document the presence and extent of pancreatic inflammation, fluid collections and necrosis according to the definitions given in the revised Atlanta criteria (20). As an integrated part of the CT exam at day 5 (+/- 1 day) patients will undergo assessment of the colon/gut transit time using radiopaque markers given orally in the morning on day 3 up to the planned CT exam. Finally, the intestinal permeability will be evaluated by a polyethylene glycol (PEG) 400/4000 test (see section 9.1.5.) 48 hours after randomization. At hospital discharge, patients are invited for a follow-up visit on day 14 (+/- 2 days) after randomization where the outcomes assessed during hospital admission (blood test and questionnaires including the PASS score) will be reassessed. Patients ready for discharge prior to completing five days treatment with methylnaltrexone will be handled according to the following:

- < 48 h of treatment: All data collection will be terminated upon discontinuation of the study medication and participant is regarded as dropout.

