2.5. Specification of endpoints

The primary outcome at the primary endpoint will be analyzed by intention-to-treat (ITT), whereas the secondary endpoints will be per-protocol (PP) analyses. Several factors such as treatment effect of methylnaltrexone and possible side-effects (17) may lead to an uneven distribution between excluded patients in the treatment groups (e.g. if methylnaltrexone patients are discharged earlier or discontinue treatment due to side effects). The ITT-analysis will protect against the potential bias of excluding patients unevenly according to which treatment they received. Only if the participant is randomized but never receives treatment, will they be excluded from the ITT-analysis.

The PP-analysis aims to uncover the treatment effect under ideal conditions in terms of treatment duration and follow-up. Furthermore, the PP-analysis is expected to provide mechanistic insights into the role of opioids and opioid antagonism in acute pancreatitis. Participants are included in the PP-analysis, when:

1. > 75 % of the study drug has been given
2. No major protocol deviations have been recorded

The trial is designed as a superiority trial, and we expect to see an effect of treatment after 48 hours of treatment – which is the explanation for choice of primary endpoint. Thus, we expect that the group allocated to the methylnaltrexone treatment, compared to the usual care group, will have:

1. Reduced disease severity (lower PASS-scores, lower prevalence of severe disease)
2. Improved clinical outcomes (lower pain scores, shorter admission lengths, reduced mortality, inflammatory cytokines/intestinal permeability/transit times closer to normal range, reduced prevalence of pancreatic complications)

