3.2. Randomization and Blinding

The Hospital Pharmacy at Herlev Hospital, Denmark, will conduct randomization in random block sizes without stratification (block-randomization) using statistical software approved for

this purpose, e.g. from the website www.randomization.com. Dropouts (treatment with study medication less than 48 hours) will be replaced by new subjects, and a mirror-randomization will be performed.

Labelling will also be performed by the Hospital Pharmacy at Herlev Hospital, according to Annex 13 of the Good Manufacturing Practice guidelines of the International Conference on Harmonization-GCP guidelines and local law. The study medication will be delivered directly to the respective trial sites by the Hospital Pharmacy at Herlev Hospital in vials labelled with the randomization number corresponding to the allocation and the information that it is intended for use in a clinical trial only. Each vial contains 0.6 ml of transparent fluid corresponding to 12 mg methylnaltrexone or matching volume of Ringer's Lactate.

A list of randomization numbers is devised by the Hospital Pharmacy at Herlev Hospital and provided to trial personnel. After inclusion, a randomization number is assigned to the individual trial participant as instructed by the Hospital Pharmacy.

4. Study Population

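### The primary PASS is timed from randomization but the dropout and replacement rule counts hours of treatment, so a patient with an observed 48-hour score can be replaced and cut from follow-up

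*SAP*

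**What the plan says.** **Endpoint clock.** Protocol 7.4.1 defines the primary endpoint as the PASS difference "between the methylnaltrexone group and the placebo group 48 hours after randomization". SAP 2.5.1 agrees: "The primary endpoint will be assessed 48 hours after randomization". Table 1 in Protocol 7.5.1 puts a window of 2 hours either way around that visit.

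**Rationale clock.** SAP 2.5 explains the time point by treatment duration: "we expect to see an effect of treatment after 48 hours of treatment – which is the explanation for choice of primary endpoint".

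**Dropout clock.** Protocol 7.5.1, on patients ready for discharge before five days of treatment, says: "< 48 h of treatment: All data collection will be terminated upon discontinuation of the study medication and participant is regarded as dropout". SAP 6.3 (Table 2) repeats the rule. SAP 3.2 adds: "Dropouts (treatment with study medication less than 48 hours) will be replaced by new subjects". Protocol 8.2 also provides for replacement by mirror randomization.

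**Analysis set.** SAP 2.5 removes from the intention-to-treat set only patients who were randomized but never treated.

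**Start of infusion.** The only limit is in Protocol 7.3.1: "the continuous infusion of study medication will be started no later than 24 hours after preparation". The same section describes treatment as given "intravenously for the first 5 days of admission", whereas Protocol 7.7 has patients approached on admission or later during the stay.

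**The concern.** The endpoint, its justification and the dropout rule agree only if infusion begins at the moment of randomization, which neither document requires. Once there is a gap, a patient can supply the primary outcome on schedule and still be classed as a dropout.

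What is at stake is less the 48-hour score than what happens to the patient afterwards. SAP 6.3 expects early discharge to reflect early recovery. SAP 2.5 warns that early discharge or stopping may be uneven between arms and relies on intention to treat to protect against it. A rule that ends follow-up and brings in a new patient because someone left early acts on a post-randomization outcome that treatment may influence. It therefore works against that protection.

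**Working it through.** **1. The plan's own figure.** From Protocol 7.6 and SAP 3.1: difference 25, SD 40, two-sided alpha 0.05, power 80 %.

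n = 2 × [40 × (1.960 + 0.842) / 25]² = 40.19, rounded up to 41 per group. The stated 41 reproduces. With 45 per group, power = Φ(25 × √(45/2) / 40 − 1.960) = 84.2 %. The sample size itself is not in question.

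**2. Is the start delay d bounded?** Study drug carries the randomization number (Protocol 8.1, SAP 3.2), so the first bag is prepared after randomization. The 24 hours in Protocol 7.3.1 run from preparation. No limit is written for randomization to preparation. Table 1, however, counts from randomization and ends the study at 120 ± 2 h, and treatment lasts 5 × 24 = 120 h. Five full infusions fit only if d + 120 ≤ 122, so d is at most about 2 h. A 24-hour delay would end the fifth infusion at 144 h. The schedule implies a prompt start but does not state one.

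**3. Where the clocks collide.** A patient who stops at hour t after randomization has had t − d hours of treatment. The dropout label applies when t − d < 48, that is, t < 48 + d. The primary score exists if t is at or after the assessment. For a score taken at exactly 48 h, the conflict runs from 48 to 48 + d:

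| Delay d | Treatment at 48-h score | Discharge times giving both an observed score and a dropout label |
|---|---|---|
| 0 h | 48 h | none |
| 2 h | 46 h | 48 to under 50 h |
| 6 h | 42 h | 48 to under 54 h |
| 12 h | 36 h | 48 to under 60 h |

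The window allows a score at 46 h, which extends each interval by up to 2 h at its start. A small conflict then exists even at d = 0.

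**4. What happens to such a patient.** All data collection ends and a replacement is randomized. A patient discharged just past 48 h of treatment keeps the home questionnaires, the outpatient CT offer, the 14-day visit (including PASS), and later registration of mortality. Both patients stay in the intention-to-treat set.

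**5. Exposure, as illustration only.** Assumptions: constant-rate infusion, one compartment, half-life 8.5 h (Protocol 10.2.1 gives 8–9 h), k = ln 2 / 8.5.

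- Drug given by the score: (48 − d) / 48.
- AUC(T) ∝ T − (1 − e^(−kT)) / k, compared at T = 48 − d and T = 48.
- Level at scoring: (1 − e^(−k(48−d))) / (1 − e^(−48k)).

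| d | Drug given | AUC | Level at scoring |
|---|---|---|---|
| 2 h | 96 % | 95 % | about 100 % |
| 6 h | 88 % | 84 % | 99 % |
| 24 h (worst case) | 50 % | 37 % | 88 % |

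If, as a further assumption, the effect were proportional to infusion time and every patient were delayed equally, power with 45 per group would be 81 % at 2 h (difference 25 × 46/48 = 23.96) and 74 % at 6 h (25 × 42/48 = 21.88).

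**The case against.** Randomization is the standard time origin for an intention-to-treat comparison, and a short start delay is ordinary. Table 1 points to a delay of about 2 h, for which the exposure loss is trivial and the conflict interval is short. The 48-hour score is not lost either: data collection stops on discontinuation, after the score was taken, and SAP 2.5 keeps the patient in the primary analysis. The prespecified secondary analyses are per protocol and require more than 75 % of study drug. If that means the planned five days, a patient with 42 of 120 h (35 %) would be left out of them anyway.

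Most of this stands, and it limits the point. A reader might infer from Protocol 7.3.1 that infusion may start 24 h or more after randomization, so that the score reflects half the intended exposure or less. The documents do not support that. The 24 hours limit how long prepared solution may wait, Table 1 contradicts such a delay, and even in that case the modelled level at scoring is 88 % of intended. Nor do the documents give an exposure–response relation from which dilution of the effect could be claimed.

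The objection does not remove the rule. It still replaces a patient whose primary outcome was observed, and stops the 14-day and mortality follow-up that a patient discharged slightly later would have.

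**Conclusion.** The inconsistency is real and lies in the text: one clock for the primary endpoint, another for its rationale and for dropout and replacement, and no stated link between them. With any start delay, a patient with an on-time 48-hour PASS can be labelled a dropout, lose further follow-up and be replaced, while remaining in the intention-to-treat set. The interval in which this can occur is as long as the delay, plus up to 2 h from the visit window.

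How many patients fall in it cannot be computed, because neither document gives start delays or the distribution of discharge times. The exposure and power figures are illustrations resting on the assumptions stated with them. This is a matter of consistent rules and complete follow-up, not a demonstrated loss of power. Two limits on the reading: Table 1 was available only as converted text, so its treatment span is uncertain, and the SAP's schedule figure was not available.

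**What to change.** 1. Keep randomization as the time origin of the primary endpoint. Moving it to first infusion is debatable and not needed here.
2. In Protocol 7.5.1 and 8.2 and SAP 3.2 and 6.3, define the dropout and replacement rule on the endpoint's clock, so that no patient whose 48-hour PASS was observed within its window is classed as a dropout, replaced or cut from follow-up.
3. Add the randomization-to-first-infusion interval to SAP 2.4 and report it by arm. Protocol 7.3.1 already records infusion start.
4. Reconcile the time origins in Protocol 7.3.1 (days of admission), 7.5.1 and Table 1 with those in SAP 2.5, 2.5.1, 3.2 and 6.3. Whether to set a maximum interval, and its value, is for the sponsor.

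**Cost.** Wording only, with no new type of visit. The few patients affected would receive the follow-up already planned for later discharges, and fewer replacements would be needed. The downside is that some patients with slightly under 48 h of treatment count as completers for the primary endpoint; the reported interval will show by how much.

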2.5.2. Secondary Endpoints

The secondary and exploratory endpoints are assessed at baseline, daily during treatment and at 14-day follow-up.

3. Study Design

This is a multicenter, investigator-initiated, double-blind, 1:1 randomized, placebo-controlled interventional, parallel-group, superiority trial, that will be conducted at four referral centers for acute pancreatitis in Denmark (Aalborg University Hospital, Odense University Hospital, Copenhagen University Hospital Hvidovre, and Bispebjerg Hospital). The Danish regulations have approved the trial: The North Denmark Region Committee on Health Research Ethics (Identifier: N-20200060) and the Danish Medicines Agency (EudraCT identifier: 2020-002313-18). We plan to prospectively include 90 patients admitted with predicted moderate-to-severe acute pancreatitis. Written informed consent will be obtained from all participants prior to any trial-specific procedures. Patients entering the study, will be randomized 1:1 to receive 5 days of intravenous methylnaltrexone or matching placebo, during admission. While participating in the study, patients will receive standard treatment according to guidelines and no concomitant medication is prohibited. After discharge patients will be invited to complete a 14-day follow. In addition to treatment with PAMORA, patients will undergo a series of examinations daily during treatment and at the 14-day follow-up, according to figure 2.

[figure not shown]

Figure 2

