#### 6.1.1. Study medication

In this study, the effects of PAMORA on disease development and progression in patients with AP will be investigated. Patients with AP will be administered Methylnaltrexone (Relistor®) intravenously. This medication is defined as the investigational product. Relistor® is approved and sold on the Danish marked for treatment of opioid-induced constipation. This PAMORA have not previously been investigated in patients with pancreatitis. The dose regimes for this study will be according to label. Please see the Summary of Product Characteristics for further details. For detailed description of possible side effects, see section 11.2. We have previously shown, in patients with opioid-induced obstipation and healthy subjects, that opioid antagonism incl. PAMORA treatment increases gut motility, relaxes gastrointestinal sphincters, increases the intestinal water content and improves the immune response, without affecting analgesia (10,12–15). The affinity of PAMORAs to the  $\mu$ -opioid receptors is much stronger than opioid analgesics. Therefore, they as antagonists have the potential to counteract the harmful effects of opioids on the gut mucosa, bacterial translocation and inflammation despite the high levels of exogenous opioids present in patients with pancreatitis. PAMORAs do not cross the blood-brain barrier and consequently do not interfere with analgesia or other central effects of opioids (12).

We hypothesize that treatment with the PAMORA methylnaltrexone will antagonize the harmful effects of opioids without reducing analgesia in patients with AP and hence reduce disease severity and improve clinical outcomes. If successful, this sub-study will for the first time document the effects of a targeted pharmacotherapy in AP with the potential benefit of improved patient outcomes.

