#### 7.2.2. Exclusion criteria

- Definitive chronic pancreatitis according to the M-ANNHEIM criteria (21) -
- Known allergy towards study medication
- Known or suspected major obstruction or perforation of the intestines
- Toxic megacolon
- Known or suspected abdominal cancer (incl. intestine, pancreas and the biliary tree)
- Pre-existing renal insufficiency (defined as habitual estimated glomerular filtration rate (eGFR) below 45 ml/min/1,73m^2)
- End-stage renal impairment requiring dialysis prior to inclusion
- Severe pre-existing comorbidities (assessed by investigator upon inclusion)
- Severe non-pancreaticobiliary infections or sepsis caused by non-pancreaticobiliary disease
- Child-Pugh class B or C liver cirrhosis
- Females that are currently lactating

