#### 7.3.4. Concomitant medication and care

Patients participating in the study will receive supportive treatment according to the IAP/APA evidence-based guidelines for the management of AP (2) as prescribed by the treatment-responsible physician. This includes supportive therapy with intravenous fluid therapy (Ringer's lactate 5-10 ml/kg per hour), enteral feeding (elemental or polymeric enteral nutrition formulations via nasojejunal or nasogastric route, alternatively parenteral if nasojejunal tube feeding is not tolerated) and analgesics. As the patients will be admitted during participation in the study, all concomitant medication and care will be registered in the patient's medical files as with any other patient and subsequently transferred to the CRF. This specifically includes a detailed quantification of the need for analgesics (separated into opioids and non-opioids) as this is of great clinical significance.

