### 7.4.2. Secondary endpoints

- Difference in daily **PASS scores** between subgroups
- Difference in daily assessments of circulating **pro- and anti-inflammatory markers** (including CRP, IL-6, IL-8, IL-18, TNF- $\alpha$  and CD163) as well as **intestinal barrier markers** between subgroups
- Difference in **intestinal permeability** between subgroups measured from 48 to 72 hours after randomization using the oral polyethylene glycol 400/4000 test
- Difference in **intestinal motility** assessed by means of gut/colon transit using a CT-based radiopaque marker method on day 5 (+/- 1 day) between subgroups
- Difference in **pancreatic complications** (e.g. edema, fluid collections and necrosis) assessed and quantified with contrast-enhanced CT on day 5 (+/- 1 day) after randomization (20)
- Difference between subgroups in the following **clinical outcome parameters**: pain intensity and gut function (assessed by questionnaires), quantification of analgesics (separated into opioids and non-opioids), need for nutritional support, disease severity, invasive treatments, intensive care and hospital stay, as well as mortality during total hospitalization
- Difference in **health resource utilization** during hospitalization between subgroups

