### 8.2. Blinding

The study is double-blinded, and the blinding will be conducted by the Hospital Pharmacy at Herlev Hospital. This way of blinding will ensure that personnel involved in the project and participants included in the study are prevented from knowing information that might lead to bias of the results. All study medication will be labelled indicating “study medication”, “id”, “initials”, “period”, “daily dosing paradigm” and “contact information”. Labelling will be performed by the Hospital Pharmacy at Herlev Hospital, according to Annex

13 of the Good Manufacturing Practice guidelines of the European Commission, ICH, GCP guidelines, and local law.

In case of an medical emergency (e.g. SUSAR, see section 10.2.3.) that necessitates knowledge of the treatment randomization, the individual treatment assignment for each subject will be available at each study center in sealed envelopes (provided by The Hospital Pharmacy) stored in a secure area accessible to study personnel allowed by the investigator to open the code for a single subject. The other study centers can always get in contact with the primary study center by a provided phone number in case of a situation where unblinding is necessary. This procedure allows unblinding of individual subjects, without revealing codes of the entire study. Thus, the study personnel will be able to determine which treatment a particular subject was given by opening the sealed envelope with the corresponding randomization number. The investigator must state the reason why the code was broken on the envelope, date and sign it.

A subject that discontinues will be asked about the reason(s) for discontinuation and the presence of any adverse events but are not obliged to provide this information. If needed, they will be seen and assessed by a medical doctor affiliated with the study. Dropouts will be replaced by new subjects and a mirror randomization will be performed i.e. they are part of the same randomization, but with a new number (e.g. 101 replaces 1 etc.).

Patients with AP will be admitted while participating in the study and hence have the study medication (Relistor® or matching placebo) administered to them by medical professionals. The medication and placebo will be delivered to the medical staff from the Hospital Pharmacy at Herlev Hospital in the form of fluid for infusion with similar appearance, so that the medical staff treating the patient will remain blinded.

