#### 9.1.6. PEG 400/4000 test

Measurement of intestinal permeability and mucosal integrity in patients with AP, will be performed using the oral PEG 400/4000 test (30). In case of intestinal barrier function loss (a leaky gut), the large size molecules (PEG 4000) cross the intestinal barrier, appear into the circulation and becomes detectable in urine after renal excretion. The small size molecules (PEG 400) traverse the intestinal barrier freely, independent of barrier function loss, but is affected in the same way as the large molecules by the pre- and post-mucosal processes including gastric dilution, gastrointestinal motility, bacterial degradation, and renal function. Therefore, the ratio of the urinary concentration of both molecules (PEG 400/4000) more accurately reflect the intestinal permeability and integrity than isolated measurement of a single molecule (31). A PEG solution containing 5 g PEG 400 and 5 g PEG 4000 dissolved in 100 mL water, will be prepared. 48 hours after randomization, the PEG solution is enterally administered via oral intake or a feeding tube and followed by 24-hour urine output collection. Upon collection urine will be homogenized and centrifuged. The supernatant will be desalted by ion-exchange and transferred in aliquots to vials labeled with the protocol number (PAMORA\_2020), subject number, and date of sample collection, which will subsequently be frozen and stored at approximately -80°C or cooler at the respective inclusion sites. Urine samples will be analyzed at a central laboratory to measure the analytes of interest. Excess urine samples will be kept frozen for future research purposes, thereby establishing a biobank. All samples will be destroyed at the latest 15 years after termination of the study. Ethics according to "databeskyttelsesforordningen" and "databeskyttelsesloven" will be ensured in this regard.

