For patients with acute pancreatitis, pain is the dominant symptom and thus they are exposed to increased amounts of both endo- and exogenous opioids. Opioid administration is known to cause opioid-induced bowel dysfunction primarily by binding μ -opioid receptors in the enteric nervous system (3,4). Thus, opioids promote dysmotility and prolonged gut transit time, which together can cause small intestinal bacterial overgrowth (4). Furthermore, opioids may increase intestinal permeability, resulting in the translocation of bacteria from the gut to the peripancreatic tissue and systemic circulation. Potentially, translocation of bacteria may lead to local and systemic infections, which further may be facilitated by opioid-induced immunosuppression (5,6). Opioids also affect the pancreas directly by decreasing fluid secretion in the pancreatic duct system and increasing the frequency of contractions in the sphincter of Oddi (4,7). This may lead to decreased wash-out of intrapancreatic activated enzymes and thus worsen autodigestion of the tissue and subsequent inflammation of the pancreas. Peripherally acting μ -opioid receptor antagonists (PAMORAs) bind to the μ -opioid receptor with an affinity much stronger than opioid analgesics and thus have the potential to counteract harmful effects of opioids despite high levels of exogenous opioids in patients with pancreatitis.

We hypothesize that treatment with the PAMORA methylnaltrexone will reduce disease severity in patients with acute pancreatitis, compared to placebo. We plan to test this hypothesis by treating patients admitted with acute pancreatitis with methylnaltrexone or placebo in a 1:1 randomization design.

2. Study Objectives, Hypothesis and Outcomes

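### SAP 3 prohibits no concomitant medication, so open-label methylnaltrexone or another PAMORA is allowed in both arms; the likely effect on the primary endpoint is small, but the rule works against the trial's own contrast

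*SAP*

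**What the plan says.** SAP section 3 (Study Design) gives the rule for background treatment: "patients will receive standard treatment according to guidelines and no concomitant medication is prohibited". Protocol 7.3.4 describes guideline-based supportive care (fluids, feeding and analgesics) prescribed by the treating physician. It names no restricted drug and requires recording: "all concomitant medication and care will be registered".

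The exclusion lists in protocol 7.2.2 and SAP 4.1 refer to the trial drug in one item only, "Known allergy towards study medication". Neither list mentions current use of methylnaltrexone or another PAMORA. The discontinuation rules in protocol 7.3.2 do not cover it either.

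Protocol 6.1.1 states that the product "is approved and sold on the Danish marked for treatment of opioid-induced constipation". The SAP's background text, before section 2, says of patients with acute pancreatitis that "they are exposed to increased amounts of both endo- and exogenous opioids".

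SAP 2.5 admits a participant to the per-protocol set if more than 75% of study drug was given and no major protocol deviation was recorded. SAP 6.3, which is headed Major Protocol Deviations, deals only with early discharge and missing values.

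**The concern.** The trial tests an opioid antagonist against none. A rule that leaves every concomitant drug open also leaves the test drug open, in a population whose opioid exposure brings it close to the marketed indication. As written, a patient admitted on a PAMORA is eligible and may continue it, and a constipated patient in either arm may be given the marketed product.

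Three consequences follow.

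- **Placebo arm.** Use before 48 hours moves placebo PASS scores toward those of the active arm and shrinks the primary contrast. Use that starts after 48 hours cannot affect the primary endpoint. It can still dilute permeability, which is "measured from 48 to 72 hours after randomization using the oral polyethylene glycol 400/4000 test" with the test dose "followed by 24-hour urine output collection", and gut transit, which is read from CT at about day 5.
- **Active arm.** Study drug is supplied in a form chosen "so that the medical staff treating the patient will remain blinded". Staff who prescribe an open-label dose cannot tell whether it comes on top of active infusion.
- **Per-protocol set.** SAP 2.5 wants this set to give mechanistic insight into opioid antagonism. A placebo patient taking an opioid antagonist works directly against that purpose.

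**Working it through.** **1. Is the drug restricted anywhere?**

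| Place | Subject | Restricts a PAMORA? |
|---|---|---|
| SAP 3 | Concomitant medication | No; states that nothing is prohibited |
| Protocol 7.3.4 | Concomitant care | No; requires recording |
| Protocol 7.2.2 and SAP 4.1 | Exclusions | No; allergy only |
| Protocol 7.3.2 | Discontinuation | No |
| SAP 2.5 and 6.3 | Per-protocol set, deviations | No; permitted use is not a deviation |

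**2. Reproduce the planned sample size.** Inputs from protocol 7.6 and SAP 3.1: difference 25, SD 40, power 80%, two-sided alpha 0.05.

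n = 2 × (1.960 + 0.842)² × 40² / 25² = 2 × 7.849 × 2.56 = 40.2, rounded up to 41 per group. This matches the plan. The calculations below use 45 per group, because that is the enrolment target, dropouts are replaced (protocol 8.2, SAP 3.2) and collection runs to 90 full datasets (protocol 9.3.1).

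**3. Dilute the difference.** Let c be the share of placebo patients who receive an antagonist before 48 hours and f the share of the 25-point effect that they obtain. The expected difference is 25 × (1 − c × f). Both c and f are assumptions. Taking f = 1 is an upper bound. The SD is held at 40.

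Power is from the two-sample t-test with 88 degrees of freedom and noncentrality equal to the difference / (40 × √(2/45)) = difference / 8.433.

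| Placebo patients affected (f = 1) | Difference | Noncentrality | Power |
|---|---|---|---|
| 0 of 45 | 25.00 | 2.965 | 83.5% |
| 1 of 45 | 24.44 | 2.899 | 81.8% |
| 2 of 45 | 23.89 | 2.833 | 80.0% |
| 5% | 23.75 | 2.816 | 79.6% |

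Power reaches 80% at c = 4.5% with full effect, or at c = 8.9% (four of 45) with half effect.

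**4. Allow for baseline adjustment.** SAP 6.1 adds baseline PASS as a covariate to the mixed model. It then names a t-test or Mann-Whitney test at 48 hours without saying whether that test is adjusted. For an adjusted contrast, the SD becomes 40 × √(1 − r²) and one degree of freedom is lost. The documents give no baseline correlation r, so two values are assumed, with f = 1.

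| r | SD | None | 1 of 45 | 2 of 45 | 80% reached at c = |
|---|---|---|---|---|---|
| 0.3 | 38.16 | 86.7% | 85.2% | 83.6% | 8.8% |
| 0.5 | 34.64 | 92.3% | 91.2% | 89.9% | 17.2% |

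Across both versions, one or two affected patients cost about 1 to 3.5 points of power. In the full-effect case the expected difference shrinks by 0.56 or 1.11 points out of 25.

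**The case against.** The strongest reply is that the problem is hypothetical. That the drug is marketed and that patients receive opioids does not show that anyone would give a PAMORA within 48 hours of randomization in acute pancreatitis, an indication that protocol 6.1.1 says is untested. The guideline care listed in protocol 7.3.4 does not include one. Two fully affected placebo patients still leave the 80% target, and full effect presumes that any antagonist, at any dose or route, works like the trial infusion. All of this stands, and it limits the size of the point.

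It is also true that staff who know a patient is in the trial have reason not to add the same drug, that concomitant medication is recorded in the CRF, and that the primary analysis is by intention to treat. These lower the risk and let use be described afterwards. They do not remove the permission, and recording does not bring the patient out of the per-protocol set.

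Leaving background care unrestricted in acutely ill inpatients is a legitimate choice in general. The plan gives no reason for extending it to the drug under test.

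Stronger readings are tempting and should be resisted:

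- A reader might infer that the primary result is in jeopardy, for example by assuming 20% use. That is nine of 45 placebo patients, and nothing in the documents supports such a rate.
- A reader might infer that a secondary endpoint is seriously exposed through permeability and transit. Protocol 7.4.2 lists them as secondary, but SAP 2.3 makes them exploratory.
- A reader might want patients on opioid/naloxone combinations excluded. No passage shows that those products act like the intravenous study drug.
- A reader might infer that laxatives containing polyethylene glycol would disturb the PEG test. The documents do not discuss this, and it is a separate question.

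**Conclusion.** The point holds as a gap in the rules. The plan affirmatively permits the drug under test, and its class, outside randomized treatment, and no other provision narrows that permission. The direction of any bias in the placebo arm is known: toward no difference. The active arm carries a risk of duplicate dosing under blinding, and the per-protocol definition does not remove affected patients.

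The size is small for the primary endpoint. It rests on an assumed one or two placebo patients treated before 48 hours and an assumed full effect in each; lower use or a partial effect makes the loss smaller still. The documents do not support a claim that such use will occur, or that it would change the trial's conclusion. The case for change is that the rule serves no stated purpose and is cheap to correct.

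**What to change.** 1. Replace the phrase in SAP 3, and add to protocol 7.3.4: *Open-label methylnaltrexone or other peripherally acting opioid antagonists are not given during the study-drug period; naloxone for emergency opioid reversal is allowed, and constipation is managed with laxatives.*
2. State in protocol 7.2 and SAP 4.1 that a patient already taking a PAMORA must stop it or not be enrolled.
3. State in SAP 2.5 and 6.3 that a patient who nevertheless receives one stays in the intention-to-treat analysis, and that such use is a major protocol deviation for the per-protocol set.
4. Report use by arm from the concomitant medication already in the CRF.

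No new data are needed. The medication rule and the eligibility condition probably count as a significant modification, which under protocol section 11 needs approval from the ethics committee and the Danish Medicines Agency. One drug class is withheld for 5 days, and a few patients may not be enrolled. If an amendment is unwelcome, item 4 can be done by an SAP edit alone, but it describes use without preventing it.
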